7.3 Subject Population(s) for Analysis

- All-treated population: Any subject randomized into the study that received at least one dose of study drug
- Protocol-compliant population: Any subject who was randomized and received the protocol required study drug exposure and required protocol processing

8 Safety and Adverse Events

8.1 Definitions

Unanticipated Problems Involving Risk to Subjects or Others

Any incident, experience, or outcome that meets all of the following criteria:

- Unexpected in nature, severity, or frequency (i.e. not described in study-related documents such as the IRB-approved protocol or consent form, the investigators brochure, etc)
- Related or possibly related to participation in the research (i.e. possibly related means there is a reasonable possibility that the incident experience, or outcome may have been caused by the procedures involved in the research)
- Suggests that the research places subjects or others at greater risk of harm (including physical, psychological, economic, or social harm).

Adverse Event

An **adverse event** (AE) is any symptom, sign, illness or experience that develops or worsens in severity during the course of the study. Intercurrent illnesses or injuries should be regarded as adverse events. Abnormal results of diagnostic procedures are considered to be adverse events if the abnormality:

- results in study withdrawal
- is associated with a serious adverse event
- is associated with clinical signs or symptoms
- leads to additional treatment or to further diagnostic tests
- is considered by the investigator to be of clinical significance

Serious Adverse Event

Adverse events are classified as serious or non-serious. A serious adverse event is any AE that is:

- fatal
- life-threatening
- requires or prolongs hospital stay
- · results in persistent or significant disability or incapacity
- a congenital anomaly or birth defect
- an important medical event

Important medical events are those that may not be immediately life threatening, but are clearly of major clinical significance. They may jeopardize the subject, and may require intervention to prevent one of the other serious outcomes noted above. For example, drug overdose or abuse, a seizure that did not result in in-patient hospitalization, or intensive treatment of bronchospasm in an emergency department would typically be considered serious.

All adverse events that do not meet any of the criteria for serious should be regarded as *non-serious* adverse events.

Adverse Event Reporting Period

The study period during which adverse events must be reported is normally defined as the period from the initiation of any study procedures to the end of the study treatment follow-up. For this study, the study treatment follow-up is defined as 30 days following the last administration of study treatment.

Preexisting Condition

A preexisting condition is one that is present at the start of the study. A preexisting condition should be recorded as an adverse event if the frequency, intensity, or the character of the condition worsens during the study period.

General Physical Examination Findings

At screening, any clinically significant abnormality should be recorded as a preexisting condition. At the end of the study, any new clinically significant findings/abnormalities that meet the definition of an adverse event must also be recorded and documented as an adverse event.

Post-study Adverse Event

All unresolved adverse events should be followed by the investigator until the events are resolved, the subject is lost to follow-up, or the adverse event is otherwise explained. At the last scheduled visit, the investigator should instruct each subject to report any subsequent event(s) that the subject, or the subject's personal physician, believes might reasonably be related to participation in this study. The investigator should notify the study sponsor of any death or adverse event occurring at any time after a subject has discontinued or terminated study participation that may reasonably be related to this study. The sponsor should also be notified if the investigator should become aware of the development of cancer or of a congenital anomaly in a subsequently conceived offspring of a subject that has participated in this study.

Abnormal Laboratory Values

A clinical laboratory abnormality should be documented as an adverse event if any one of the following conditions is met:

- The laboratory abnormality is not otherwise refuted by a repeat test to confirm the abnormality
- The abnormality suggests a disease and/or organ toxicity
- The abnormality is of a degree that requires active management; e.g. change of dose, discontinuation of the drug, more frequent follow-up assessments, further diagnostic investigation, etc.

Hospitalization, Prolonged Hospitalization or Surgery

Any adverse event that results in hospitalization or prolonged hospitalization should be documented and reported as a serious adverse event unless specifically instructed otherwise in this protocol. Any condition responsible for surgery should be documented as an adverse event if the condition meets the criteria for and adverse event.

Neither the condition, hospitalization, prolonged hospitalization, nor surgery are reported as an adverse event in the following circumstances:

- Hospitalization or prolonged hospitalization for diagnostic or elective surgical procedures for a
 preexisting condition. Surgery should *not* be reported as an outcome of an adverse event if the
 purpose of the surgery was elective or diagnostic and the outcome was uneventful.
- Hospitalization or prolonged hospitalization required to allow efficacy measurement for the study.
- Hospitalization or prolonged hospitalization for therapy of the target disease of the study, unless it
 is a worsening or increase in frequency of hospital admissions as judged by the clinical
 investigator.

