1.6.2 Other Risks of Study Participation

To minimize any potential risk, a physician and a research nurse will be present and monitor all procedures. Careful and continuous monitoring of vital signs, blood chemistries, 12-lead echocardiograms and adverse events will help minimize potential risks. Confidentiality will be maintained for the identity of participants in this study, except as necessary for oversight by the Secretary of the Department of Health and Human Services or his designated representative. To minimize the theoretical risk of rebound hypertension following abrupt carbidopa withdrawal, prior to wash-out, between crossovers, we will reduce the dose of study medication by 2/3 for one day (the day of the office visit) and then to 1/3 the following day. We will monitor adverse events with a phone call on the first day of adjusting dosages, and at weekly intervals thereafter. We will emphasize to patients and caregivers the importance of contacting the Center should they experience a change in their health status. We will also collect daily diaries prompting patients/caregivers to write down adverse events. To minimize the potential risks of orthostatic hypotension, we will provide patients with a practical advice sheet to quickly raise blood pressure including to lay supine (to aid venous return), ensure good hydration (consume 500 ml of water) and be cognitively aroused (doing something they enjoy, talking, homework, playing with a computer game console which raises blood pressure).

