3.1 General Design

Double-blind, Randomized, placebo control; cross-over design

[figure not shown]

Fig. 7: Overall trial design: This is a 14-week study. Patients will receive, in random order, high dose carbidopa (600mg/day), low dose carbidopa (300 mg/day) or placebo. Between each crossover, there will be a titration down over 2-days followed by a 2-day washout. An interim safety phone call will be made 7-days after crossover. Safety bloods will be collected each study visit. Patients participating in telemedicine visits will be given prescriptions to collect their safety bloods and urine locally. Adverse events will be monitored throughout by weekly phone calls and a daily symptom diary log. There will be 4 evaluation visits (in the office or via 2-way teleconferencing), 28 days apart and another follow-up phone call 7-days after completing the study. See text for details. A 14-day window either side of scheduled office visits will be allowed to accommodate school/work commitments. Because patients with FD are prone to frequent illnesses as part of their underlying medical condition, we will allow patients undergoing medical care for an unanticipated/unexpected adverse event to cease taking the study medication and resume again when the issue is resolved and/or the patient is recovered. In all instances, this will be documented in the case report forms.

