5.9.4 Return or Destruction of Study Drug

At the completion of the study, there will be a final reconciliation of drug shipped, drug consumed, and drug remaining. This reconciliation will be logged on the drug reconciliation form, signed and dated. Any discrepancies noted will be investigated, resolved, and documented prior to return or destruction of unused study drug. Drug destroyed on site will be documented in the study files.

6 Study Procedures

Table 1 provides a complete list of the procedures at each study visit (in the office or via telemedicine 2-way conferencing) and figure 7 provides a timeline for the procedures at visits.

Table 1: Study procedures

Table 1. Study procedures	\/:a:4.4	Violt 0	Visit 3	Visit 4
	Visit 1	Visit 2	VISIT 3	VISIT 4
Procedure	Baseline/R	Crossover 1	Crossover 2	Final
Consent/ascent	Ø			
Urine pregnancy test (reproductive females)	Ø			Ø
Inclusion/exclusion criteria	Ø			
Concomitant medications/compliance check	Ø	Ø	Ø	Ø
Vital signs (temperature, weight)	✓	₫	✓	Ø
Metabolic panel	Ø	Ø	\square	Ø
Urinalysis	v	\square	\square	V
CBC	V	\square	V	\square
12-lead ECG*	V	\square	V	Ø
Physical/neurological examination	v	\square	\square	V
Adverse event questioning	V	\square	V	\square
OH-Questionnaire	Ø	\square	Ø	☑
24-h ambulatory BP recording	Ø	\square	\square	☑
24-h urine catecholamine excretion	V		V	Ø
Supine/seated/standing BP	V		V	Ø
Beat-to-beat BP or HR at rest	V		V	Ø
Beat-to-beat BP during Stroop (Office)	V		V	Ø
HR with serial 7s subtractions (Virtual Visit)	✓	✓	Ø	Ø
Symptom/AE diary collection		\square		\square
Dose de-escalation		Ø	\square	Ø
Washout		Ø	Ø	
Dose adjustment day safety phone call		Ø	Ø	
Day 7 adverse event monitoring phone call	Ø	Ø	Ø	☑

CBC; complete blood count, ECG; electrocardiogram, BP; blood pressure, AE, adverse event; R; randomization.

Visit 1. Baseline/Randomization:

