At this visit, supine/seated/standing BP and beat-to-beat changes during stoop will be measured 3-h post dose or heart rate during serial sevens testing. Ambulatory recordings will be calibrated against office blood pressure readings for in-office visits and will be downloaded and reviewed for data quality. Safety bloods and 12-lead ECG will be obtained and physical examination will be conducted. Patients will be questioned about adverse events and score the OH-Q. They will be crossed over to receive their final treatment allocation, depending on their randomization sequence. Dosing instructions will be provided to titrate down for 2-days and washout for 2-days. Patients will be asked to maintain their symptom diary and return for follow-up in 4-weeks with a 24-hour urine collection and ambulatory BP recording and the symptom diary. As described for visit 2, patients will be contacted on the day that they begin their new treatment and seven days after being on their treatment. Thereafter, we will contact patients on a weekly basis to monitor potential adverse events. Patients will return for follow-up after 28-days of treatment bringing with them a 24-hour ambulatory recording and a 24-h urine collection. These visits may be performed virtually, with the standard operating proceedures outlined in Figure 8. They will be instructed to continue documenting their symptom in the custom diary.

Visit/Televisit 4. Final:

At the final study visit or televisit (see Fig 8 for details), 3h post-dose we will conduct the orthostatic blood pressure measurements supine/seated/standing while obtaining concomitant measurements of blood pressure of the ambulatory monitor or using the ambulatory monitor for televisit patients. Vital signs and Stroop-induced changes in BP will be assessed in office or heart rate monitoring via the iPhone application while performing

serial sevens will be done during the televisit. We will obtain safety bloods, urinalysis, a 12-lead ECG and all patients will undergo a physical and neurological evaluation. Patients will fill the OH-questionnaire and be questioned about adverse events. Ambulatory recordings will be downloaded to check for data quality and 24-h urine collections will be assayed for catecholamines. Diaries and unused medications will be collected or returned to the Center. Dose de-escalation instructions will be provided for the end of the study.

Follow-up phone call:

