One week after completion of the cross over periods, patients will receive another follow-up phone call to monitor any adverse events.

24-hour Ambulatory Blood Pressure Monitoring:

Patients with FD frequently undergo ambulatory BP monitoring while keeping a detailed log of their activities (sleep/meal-times/medications/posture/symptoms). Compliance is excellent and they tolerate the procedure well. The majority of patients have home nursing support that will aid with fitting the ambulatory monitors at home, and we will also provide a tutorial as well as written instructions on how to fit the monitor (Appendix), including instrumentation on the non-dominant arm and the distance (in cm) from the elbow. We will use video calls to aid fitting the ambulatory monitor when necessary.

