8.2 Recording of Adverse Events

At each contact with the subject, the investigator must seek information on adverse events by specific questioning and, as appropriate, by examination. Information on all adverse events should be recorded immediately in the source document, and also in the appropriate adverse event module of the case report form (CRF). All clearly related signs, symptoms, and abnormal diagnostic procedures results should recorded in the source document, though should be grouped under one diagnosis.

All adverse events occurring during the study period must be recorded. The clinical course of each event should be followed until resolution, stabilization, or until it has been determined that the study treatment or participation is not the cause. Serious adverse events that are still ongoing at the end of the study period must be followed up to determine the final outcome. Any serious adverse event that occurs after the study period and is considered to be possibly related to the study treatment or study participation should be recorded and reported immediately.

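### Adverse events are to be recorded for 30 days after the last dose, but the last scheduled contact is at about day 7, so most of the off-drug window relies on passive reporting

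*Combined protocol and SAP*

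**What the plan says.** Section 8.1 (Adverse Event Reporting Period) runs the reporting period from the first study procedure to the end of treatment follow-up and adds that, for this study, "the study treatment follow-up is defined as 30 days following the last administration of study treatment". Section 8.2 states: "All adverse events occurring during the study period must be recorded". It also requires the investigator to ask specifically about adverse events at each contact.

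The contact schedule stops earlier:

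- Section 3.1 (Fig. 7 legend) calls this a 14-week study and ends it with "another follow-up phone call 7-days after completing the study".
- Section 6 (Follow-up phone call) says: "One week after completion of the cross over periods, patients will receive another follow-up phone call to monitor any adverse events".
- Table 1 ticks the row "Day 7 adverse event monitoring phone call" under Visit 4 and has no later column.
- Section 6 (Visit 4) has diaries collected at that visit.

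No later visit, call, diary or laboratory test is described.

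Two instructions bear on what reaches the center after that call. At Visit 1 (section 6) patients are told to contact the center about any adverse event, with no end date. At the last visit (section 8.1, Post-study Adverse Event) they are told to report later events that they or their physician think could be related to the study.

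**The concern.** The plan's standard is that all adverse events are recorded up to day 30 after the last dose. During treatment that standard is supported by weekly calls and a daily diary. After the seven-day call no scheduled contact supports it, so capture moves from asking to waiting to be told.

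Safety and tolerability is Aim 1, and adverse events head the safety measures in section 3.4. If few events are recorded between about day 7 and day 30, a reader cannot tell whether few occurred or few were reported. What is at stake is the completeness of the off-drug safety record.

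**Working it through.** **Inputs.** Three 28-day treatment periods. A 2-day de-escalation and a 2-day washout at each of two crossovers (section 1.4, Overview). A call 7 days after completion (sections 3.1 and 6). A 30-day reporting window (section 8.1).

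**Date of the last dose.** De-escalation also follows Visit 4: "Dose de-escalation instructions will be provided for the end of the study". For the crossovers, section 1.6.2 describes a taper on the visit date and the next: "we will reduce the dose of study medication by 2/3 for one day (the day of the office visit) and then to 1/3 the following". I assume the same two days apply at the end of the study, which puts the last dose one day after Visit 4.

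**The plan's own figure first.**

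- Baseline to Visit 4: 3 × 28 + 2 × (2 + 2) = 84 + 8 = 92 days = 13.1 weeks.
- To a call 7 days after Visit 4: 92 + 7 = 99 days = 14.1 weeks.
- To a call 7 days after the last tapered dose: 92 + 1 + 7 = 100 days = 14.3 weeks.

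The stated 14 weeks is reproduced when follow-up ends at the seven-day call.

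**The stated reporting window.** 92 + 1 + 30 = 123 days = 17.6 weeks.

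**Days without a scheduled contact**, as (30 − day of the call after the last dose) / 30:

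- Call 7 days after the last dose: (30 − 7) / 30 = 23/30 = 77%.
- Call 7 days after Visit 4, which is day 6 after the last dose: (30 − 6) / 30 = 24/30 = 80%.

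Against the whole 123 days the gap is 23/123 = 19% to 24/123 = 20%.

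**Where it applies.** The 30 days after periods 1 and 2 fall largely inside the next treatment period, which has calls, a diary and a visit. The gap therefore follows the final period. For patients who stop early, section 4.4.2 promises every attempt to collect follow-up data but sets no contact times. The figures above carry over to them only if the same seven-day call is assumed.

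**Balance across treatments.** The three sequences end on placebo, high dose and low dose respectively, and randomization is 1:1:1. The uncovered days therefore follow each treatment about equally often.

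**The case against.** The strongest reply is that a reporting period and a contact schedule are different things. Section 8.1 does not promise active questioning to day 30, and a reporting duty can be met by reports received. That is fair as far as it goes: this is a mismatch in ascertainment, not a strict contradiction.

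The setting also helps. This is one center that actively follows its patients (section 1.4) and describes close ties to the families (section 4.4.1). Most patients have home nursing support (section 6). Section 1.6.2 urges patients and caregivers to call about any change in health. Unresolved events are followed up (sections 8.1 and 8.2), although that does not find new ones. Carbidopa's plasma half-life is 1.3 hours and enzyme inhibition lasts up to 6 hours (section 1.5), so drug effects late in the window are less likely.

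The Fig. 7 legend also says that weekly calls monitor adverse events throughout. However, section 6 ties those calls to the treatment periods, section 8.6.1 ties them to the outpatient phase, and the legend itself names a single call after completion.

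Four stronger readings are tempting but not supported:

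- A reader might infer that only events thought related can surface after day 7. The Visit 1 instruction covers any adverse event.
- A reader might cite the estimate of around 40% with impaired cognition as undermining self-report. Section 4.3.1 gives that figure for capacity to consent. Caregivers also record events, and the same doubt would apply to a phone call.
- A reader might infer that the trial will present a 30-day safety analysis. None is specified.
- A reader might infer bias between treatments. The balance of the sequences argues against it.

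What remains is that the plan's rule covers all events to day 30 and its scheduled questioning stops at about day 7.

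**Conclusion.** The point holds as a cheap improvement to safety follow-up. About 23 to 24 of the 30 days after the last dose (77% to 80%) have no scheduled contact and depend on passive reporting, so off-drug events could be under-recorded. This rests on the call being timed from the last dose or from Visit 4, and on a two-day final taper. The 14-day visit windows in section 3.1 do not change the interval after the last dose if the call moves with the visit.

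The number of events missed cannot be estimated. The consequence is limited to the completeness of post-treatment safety data, and no error in any planned treatment comparison is shown.

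**What to change.** Add one structured adverse event call at day 30 after the last dose, using the existing call script. Apply it also to patients who discontinue early, and show it in Table 1 and in the section 3.1 timeline. If that is not wanted, reconcile the section 8.1 reporting period and the section 8.2 recording rule with the contacts in sections 3.1 and 6 and Table 1. The documents do not show which was intended.

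The cost is one phone call per patient, so 30 to 36 calls at the sample sizes named in the Study Summary and section 7.2. Each patient's follow-up lengthens by 123 − 100 = 23 to 123 − 99 = 24 days, a little over three weeks.

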8.2 Recording of Adverse Events

At each contact with the subject, the investigator must seek information on adverse events by specific questioning and, as appropriate, by examination. Information on all adverse events should be recorded immediately in the source document, and also in the appropriate adverse event module of the case report form (CRF). All clearly related signs, symptoms, and abnormal diagnostic procedures results should recorded in the source document, though should be grouped under one diagnosis.

All adverse events occurring during the study period must be recorded. The clinical course of each event should be followed until resolution, stabilization, or until it has been determined that the study treatment or participation is not the cause. Serious adverse events that are still ongoing at the end of the study period must be followed up to determine the final outcome. Any serious adverse event that occurs after the study period and is considered to be possibly related to the study treatment or study participation should be recorded and reported immediately.

8.3 Reporting of Serious Adverse Events and Unanticipated Problems

Investigators and the protocol sponsor must conform to the adverse event reporting timelines, formats and requirements of the various entities to which they are responsible, but at a minimum those events that must be reported are those that are:

- related to study participation,
- unexpected, and
- serious or involve risks to subjects or others (see definitions, section 8.1).

For Narrative Reports of Safety Events

If the report is supplied as a narrative, the minimum necessary information to be provided at the time of the initial report includes:

- Study identifier
- Study Center
- Subject number
- A description of the event
- Date of onset

- Current status
- Whether study treatment was discontinued
- The reason why the event is classified as serious
- Investigator assessment of the association between the event and study treatment

